5.3 Measuring Subject Compliance

Study drug will be administered only at the investigational site and to subjects enrolled in this clinical study under the supervision of the Investigator in accordance with the protocol and institutional practice. Administration of drug will be recorded on the eCRF/EDC. Under no circumstances is the Investigator allowed to release clinical supplies for use by another physician not named on Form Food and Drug Administration (FDA) 1572, or to administer assigned study drugs to a subject who is not enrolled in this study. Study drug will be dispensed only at the institution specified on Form FDA 1572 for US sites. For EU sites, FDA form will only be collected if permitted by the management of the participating institutions or local/national guidelines and regulations.

5.4 Drug Accountability

In accordance with current Good Clinical Practice (GCP), the investigational site will account for all supplies of annamycin. Details of receipt, storage, administration, and return or destruction will be recorded in the study drug accountability record according to the standard operating procedures of the investigational site. Copies of the study drug accountability record will be provided to the Sponsor.

At the end of the study, Moloculin Biotech, Inc., will instruct the Investigator on the return or destruction of unused medication. If any medication is lost or damaged, its disposition should be documented. Investigational supplies will be retained at the clinical site pending instructions for disposition by Moloculin Biotech, Inc., at the end of the study.

6. STUDY PROCEDURES

See [Appendix A](#) and [Appendix B](#).

6.1 Screening

The Investigator is responsible for keeping a record of all subjects screened for entry into the study and subsequently excluded. The reason(s) for exclusion must also be recorded. Written informed consent must be given before any study related diagnostic or screening procedures, unless performed as part of standard of care. The following screening procedures must be performed within 35 days prior to study entry:

1. Informed consent
2. Refractory or relapsed AML diagnosis confirmed
3. ECOG performance status ([Appendix B](#))
4. Complete medical history including documentation of all treatments given for AML, cytogenetic and molecular abnormalities obtained at diagnosis, as well as a full cardiac history including assessment of prior anthracycline exposure and calculation of potential additional exposure based on assignment to dosing cohort ([Section 4](#))
5. Physical examination including height, weight, vital signs, and oral examination
6. Electrocardiogram (ECG)
7. Blood chemistry (sodium, potassium, chloride, bicarbonate, calcium, magnesium, phosphorus, blood urea nitrogen [BUN], creatinine, glucose, albumin, total protein, alkaline phosphatase, total bilirubin, SGOT, SGPT), lactate dehydrogenase [LDH], and uric acid) with creatinine clearance to be calculated from these results
8. Complete blood count (CBC) with differential and platelet count
9. Urinalysis
10. Concomitant medications used within 30 days prior to the first dose of study drug
11. Pregnancy test (with sensitivity of at least 50 mIU/mL) for women of childbearing potential within 72 hours prior to first dose of study drug
12. MUGA or ECHO scan or ECHO strain evaluation within 2 weeks prior to first dose of study drug

6.2 Baseline (Day 1)

The subject will be seen at the scheduled baseline visit (Day 1). The Investigator will certify that the subject continues to satisfy all inclusion and exclusion criteria. If eligible, the subject will be enrolled into the study and will be assigned an identification number in sequential order of enrollment. The following baseline evaluations will be made just prior to dosing on Day 1 (unless otherwise indicated):

1. Updated medical history
2. Physical examination including weight, vital signs, and oral examination
3. ECOG performance status ([Appendix B](#))
4. Blood samples for pharmacokinetic analysis and cardiac biomarkers (troponin-I and troponin-T) collected just prior to the start of the annamycin infusion on Day 1
5. Bone marrow aspirate and peripheral blood (complete blood count, differential, and platelet count; flow cytometry is optional) within 15 days prior to the first dose of liposomal annamycin to document disease
6. Updated concomitant medications

If screening was ≥ 14 days prior to first dose of study drug, the following should be repeated:

1. Blood chemistry (sodium, potassium, chloride, bicarbonate, calcium, magnesium, phosphorus, BUN, creatinine, glucose, albumin, total protein, alkaline phosphatase, total bilirubin, SGOT, SGPT, LDH, and uric acid) with creatinine clearance to be calculated from these results
2. CBC with differential and platelet count
3. Urinalysis
4. ECG

6.3 On-Study Evaluations

6.3.1 Study Drug Administration

Dosing will be in the morning at approximately the same time each day. Subjects will be treated with a daily 2-hour intravenous infusion of liposomal annamycin for 3 consecutive days. Prophylaxis as described in [Section 3.6](#) will be administered. Antiallergic premedication with diphenhydramine at a dose of 50 mg administered intravenously must be administered before each dose of liposomal annamycin. During each period of study drug administration subjects must be observed for at least 4 to 6 hours following daily liposomal annamycin administration. The following evaluations will be conducted during the 3 days of liposomal annamycin administration (Days 1 to 3):

1. Physical examination including weight, vital signs, and oral examination on Days 2 and 3
2. Blood samples for pharmacokinetic analysis collected at predose and at 0.25, 0.5, 1, 2, 4, 8, and 24 hours after the start of liposomal annamycin infusion on Day 1 and Day 3 for 3 subjects at each dose and 6 subjects at the RP2D who complete the 3 days of dosing
3. Blood samples for cardiac biomarkers (troponin-I and troponin-T) collected at predose, at the end of infusion on Day 3, and on Day 21
4. ECG monitoring at predose and at 4 hours and 24 hours after the start of liposomal annamycin infusion on Day 1, Day 2, and Day 3 for all subjects at each dose and 6 subjects on Day 1 and Day 3 only at the RP2D who complete the 3 days of dosing, coinciding with pharmacokinetic (PK) evaluations
5. Monitoring of adverse events and review of concomitant medications and concurrent illnesses (treatment-emergent or worsening illness must be recorded as an adverse event). Evaluation of blood chemistries and blood counts daily. Over the 3 days of initial dosing, if any toxicity occurs, including blood count abnormalities, dosing should be interrupted until resolution, with rechallenge at a 25% lower dose, based on guidelines in [Sections 3.3](#) and [3.4](#). If any DLT is encountered (as defined in [Sections 3.3](#) and [3.4](#)) including any severe or life-threatening event, the subject should be discontinued from the study. These specific events include (but are not limited to) development of an anaphylactic reaction during or after the infusion or clinical or radiological evidence of left ventricular dysfunction with dyspnea and pulmonary rales, cardiomegaly, or signs of pulmonary hypertension on chest x-ray.
6. Concomitant medications

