3.2 Dosing

The initial group of 3 subjects will be treated with a 2-hour intravenous infusion of 100-mg/m²/day (Dose Level 1) liposomal annamycin daily for 3 consecutive days followed by 18 days off study drug (i.e., 1 treatment cycle = 21 days). Provided that no subject experiences a DLT (defined in [Section 3.4](#)) during the induction treatment cycle through Day 28, the ensuing group of 3 subjects will receive 120-mg/m²/day (Dose Level 2) liposomal annamycin.

The liposomal annamycin dose levels planned for investigation are outlined in [Table 3](#). The starting dose is Dose Level 1.

Table 3: Liposomal Annamycin Dose Levels

[figure not shown]
Dose Level Designation	Liposomal Annamycin Dose (mg/m ² /day) × 3 days
-1	90
1	100
2	120

For each dosing cohort, if 1 of the 3 initial subjects experiences a DLT ([Section 3.4](#)), the cohort of subjects at that dose level will be expanded to 6 subjects ([Figure 1](#)). If at least 2 of the 6 subjects experience a DLT, then 3 subjects will be treated at a lower dose. If a DLT occurs in at least 2 out of 6 subjects at Dose Level 1, the next 3 subjects will be enrolled into Dose Level -1. The MTD is defined as the highest dose of liposomal annamycin at which fewer than 2 (of a cohort of up to 6) subjects experience a DLT. The RP2D is defined as the dose to be

explored in the expansion phase portion of the study, based on the aggregate data of safety and efficacy.

Figure 1: Schematic of Dosing Plan

Liposomal annamycin will be administered for a single induction cycle.

Abbreviations: DLT = dose-limiting toxicity; HSCT = hematopoietic stem cell transplantation.

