3.3 Safety Considerations

Subjects will be hospitalized for the full 3 days of liposomal annamycin administration. If a subject experiences a DLT as defined in [Section 3.4](#), or any severe or life-threatening event occurs at any time over the first 3 days, dosing should be stopped and the subject should be permanently discontinued from the study. In addition to the DLT criteria in [Section 3.4](#), the severe or life-threatening events include (but are not limited to) development of an anaphylactic reaction during or after the infusion, clinical or radiological evidence of left ventricular dysfunction with dyspnea and pulmonary rales, cardiomegaly or signs of pulmonary hypertension on chest x-ray, or acute cardiotoxicity ([Section 3.3.1](#)).

Additional criteria for safety evaluation after the initial dose during the induction cycle includes creatinine levels increasing to 1.5 times those of baseline or liver function tests increasing to 2 times those of baseline, in which case the next dose of the study drug will be decreased by 25%. If there is further deterioration of organ function after the next dose, the subject will be permanently discontinued from the trial. If these changes are acutely 2 or 3 times those of baseline, respectively, the study drug will be held, and subjects will be monitored for resolution of these changes. If there is prompt resolution (within 2 to 5 days), a rechallenge at a 25% lower dose will be attempted, and if any additional toxicity is observed, the subject will be permanently

discontinued from the trial. If resolution takes longer than 5 days, the subject will not be rechallenged and will be permanently discontinued from the trial.

Subjects successfully completing the first 3 days of dosing will then be evaluated weekly thereafter during the induction cycle of treatment (the induction cycle consists of 21 days [3 weeks total], with the first 3 consecutive days of daily liposomal annamycin treatment followed by 18 days off of liposomal annamycin).

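### Section 6.3.1 changes dosing for any toxicity, including blood counts, by reference to Sections 3.3 and 3.4, which contain no blood-count rule; nor does the plan say how dose-reduced subjects count toward the MTD

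*Combined protocol and SAP*

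**What the plan says.** Four places in the protocol bear on what happens when a toxicity appears during the three dosing days.

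- **Section 6.3.1, item 5.** During dosing, "if any toxicity occurs, including blood count abnormalities, dosing should be interrupted until resolution, with rechallenge at a 25% lower dose". The sentence goes on to cite other sections: "rechallenge at a 25% lower dose, based on guidelines in" Sections 3.3 and 3.4. It gives no grade, threshold or time limit. The same item calls for daily chemistries and blood counts.
- **Section 3.3.** The lower tier is triggered by "creatinine levels increasing to 1.5 times those of baseline or liver function tests increasing to 2 times those of baseline". The action is stated as "in which case the next dose of the study drug will be decreased by 25" per cent, with no hold. For the upper tier, "If these changes are acutely 2 or 3 times those of baseline, respectively, the study drug will be held". Then: "If there is prompt resolution (within 2 to 5 days), a rechallenge at a 25% lower dose will be attempted". Beyond that window: "If resolution takes longer than 5 days, the subject will not be rechallenged and will be permanently discontinued". A DLT or a severe or life-threatening event ends treatment. No blood-count trigger is named.
- **Section 3.4.** The DLT criteria are Grade 3 or higher nonhematologic or extramedullary events, with exceptions, plus Hy's Law. Subjects without remission are declared not evaluable for hematological toxicity.
- **Section 3.6.2.** After an allergic reaction short of anaphylaxis, the infusion is stopped and restarted at a reduced rate once the reaction has cleared. No dose reduction is stated.

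Table 3 in Section 3.2 ("Liposomal Annamycin Dose (mg/m ² /day) × 3 days") lists 90, 100 and 120 for Levels -1, 1 and 2.

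**The concern.** A site that sees a changed blood count on Day 2 is told by 6.3.1 to interrupt and later to rechallenge at a lower dose under guidelines in 3.3 and 3.4. Neither section contains such a guideline. One site could act on any count change, another could treat counts as outside the dose rules because 3.3 does not name them, and both could claim to follow the protocol. The Synopsis foresees about seven centers, so different readings are a practical possibility.

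What is at stake is the meaning of a dose level. A 3+3 design attributes each cohort's DLT count to the dose assigned. If some subjects in a cohort received less, the MTD label describes a dose that they did not get. Neither the MTD definition (Sections 3.1 and 3.2) nor Section 10 says how such a subject is counted.

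**Working it through.** **1. The rules side by side**

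| | 6.3.1 item 5 | 3.3 | 3.4 | 3.6.2 |
|---|---|---|---|---|
| Trigger | Any toxicity, blood counts named | Creatinine 1.5× or 2×, liver tests 2× or 3× baseline | DLT criteria, no blood count | Allergic reaction |
| Action | Interrupt, then 25% lower | Lower tier: next dose 25% lower, no hold stated. Upper tier: hold, then 25% lower | DLT: discontinue (through 3.3) | Stop, restart at a slower rate |
| Time limit | None stated | 5 days (upper tier) | Not applicable | None stated |

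- *Blood counts.* 6.3.1 names them. 3.3 has no trigger for them. 3.4 makes hematological evaluability depend on remission, which is judged on marrow taken on Days 15 to 35 and so is unknown on Days 1 to 3. The cross-reference leads nowhere.
- *Other toxicities below the DLT or severe level.* 3.3 gives thresholds only for creatinine and liver tests. Allergic reactions have their own rule in 3.6.2, and it differs from 6.3.1.
- *Creatinine and liver tests.* If 6.3.1 defers to 3.3, the tiers and the 5-day limit of 3.3 apply and there is no conflict. If 6.3.1 is read on its own, action and time limit differ.

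**2. The plan's own figures**

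Maximum enrollment reproduces: 2 levels × 6 + 21 = 33. Nothing below depends on it. The plan states no expected frequency of toxicity or count changes on Days 1 to 3.

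**3. Effect of a 25% reduction on the three-day total**

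Let d be the daily dose in Table 3. I assume that a reduction, once made, stays in force.

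- Full dose: 3d
- Reduced from dose 2: d + 2(0.75d) = 2.5d, or 83.3% of plan
- Reduced at dose 3 only: 2d + 0.75d = 2.75d, or 91.7% of plan

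| Level | d | Full total | Reduced from dose 2 | Reduced at dose 3 only |
|---|---|---|---|---|
| -1 | 90 | 270 | 225 | 247.5 |
| 1 | 100 | 300 | 250 | 275 |
| 2 | 120 | 360 | 300 | 330 |

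All totals are in mg/m². The steps down between levels are 1 − 100/120 = 16.7% and 1 − 90/100 = 10%, both smaller than the 25% reduction. A Level 2 subject reduced from dose 2 receives the Level 1 total (300). A Level 1 subject reduced from dose 2 receives 250, below full Level -1 (270). A reduction at dose 3 only has a smaller effect: 330 lies between full Levels 1 and 2, and 275 is just above full Level -1.

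**4. How often a cohort would be affected**

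Let q be the probability that a subject meets the literal 6.3.1 trigger before the last dose. The documents do not give q, so it is an assumption and a range is shown. Subjects are taken as independent.

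- All three on assigned dose: (1 − q)³
- At least two of three off assigned dose: 3q²(1 − q) + q³

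| q | All 3 on dose | At least 2 of 3 off dose |
|---|---|---|
| 0.1 | 0.73 | 0.03 |
| 0.2 | 0.51 | 0.10 |
| 0.3 | 0.34 | 0.22 |
| 0.5 | 0.13 | 0.50 |

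Half of three-subject cohorts would contain at least one subject off the assigned dose when (1 − q)³ = 0.5, that is q = 1 − 0.5^(1/3) = 0.21.

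**5. Whether another section settles how such subjects count**

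Section 4.3.2 replaces subjects who withdraw for reasons other than toxicity with incomplete dosing or restaging such that safety cannot be evaluated. Section 3.1 allows case-by-case replacement when treatment stops for reasons other than drug-related events. Neither covers a subject who received three doses, some of them reduced, or one whose dosing was interrupted for toxicity and not resumed. The MTD definition refers only to the number of subjects with a DLT in the cohort.

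**The case against.** The strongest reply is that 6.3.1 does not stand alone: by citing 3.3 and 3.4 it can be taken to import their thresholds. That stands for creatinine and liver tests. A reader might infer a flat contradiction there as well, but the text does not force one. The reply fails for blood counts, because the cited sections have nothing to import.

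A reader might also infer that most subjects would miss their assigned dose, since relapsed AML often comes with abnormal counts. The documents do not support this. Section 4.1 sets no neutrophil or platelet minimum and counts are checked daily, so the trigger could be met, but no frequency is given. *Most* would need q above 0.5, which the documents neither state nor exclude. Section 8.3 defines an adverse event as a change from baseline and, for laboratory values, refers to clinical significance, so a pre-existing cytopenia need not count as a toxicity. Nor do the documents say how fast a count would fall or recover.

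Thirdly, Section 3.3 by itself can produce a 25% reduction, so the totals above are not created by the conflict. That is correct. What the literal 6.3.1 wording adds is a much wider set of subjects to whom the reduction could apply.

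Finally, administration is recorded (Section 5.3), the Safety Review Committee sees all data, and the RP2D is a judgment on aggregate data. Reduced dosing would therefore be visible. Visibility does not supply the missing rule for counting these subjects.

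**Conclusion.** The point holds in this form. For blood counts, Section 6.3.1 item 5 gives an instruction that its own cross-reference cannot complete. For other toxicities outside the renal and hepatic thresholds of 3.3 and below the discontinuation level, the trigger is undefined, and for allergic reactions 3.6.2 differs. For creatinine and liver tests the inconsistency is arguable only.

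One reduction from dose 2 moves a subject's three-day total to that of the next lower level or below it (300 against 300; 250 against 270). A reduction at dose 3 alone moves it less (330 and 275). How many subjects are affected is unknown. Over assumed q from 0.1 to 0.5, the chance that a three-subject cohort is fully on its assigned dose falls from 0.73 to 0.13. The gap in the MTD rule does not depend on q: a single dose-reduced subject is enough to raise the question of how that subject counts.

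The totals assume a reduction that persists once made. The cohort probabilities assume independence and the literal reading of 6.3.1.

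**What to change.** 1. Reconcile Sections 3.3, 3.4, 3.6.2 and 6.3.1 into one dose-modification rule stated in one place, with the other sections referring to it. For each type of event (renal, hepatic, hematologic, allergic, other) it should give the trigger, the action and any time limit. The clinical content, including whether and how blood-count changes affect dosing, is for the clinical team to decide. No dose or clinical rule is proposed here.
2. State in Section 3.2 or Section 10 how subjects with reduced or incomplete dosing count toward DLT evaluation and toward the MTD at their assigned level, and bring Section 4.3.2 into line with that.

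The cost is a wording amendment and site retraining. No visits, procedures or subjects are added.

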6.3.2 Induction Cycle

Subjects will return to the clinic weekly on Days 7, 14, and 21 during the induction cycle.

The evaluations listed below will be conducted at each weekly evaluation during the induction cycle ([Appendix A](#)):

1. Monitoring of adverse events and review of concurrent illnesses (treatment-emergent or worsening illness must be recorded as an adverse event)
2. Concomitant medications
3. Physical examination including weight, vital signs, and oral examination
4. CBC with differential and platelet count
5. Blood chemistry (sodium, potassium, chloride, bicarbonate, calcium, magnesium, phosphorus, BUN, creatinine, glucose, albumin, total protein, alkaline phosphatase, total bilirubin, SGOT, SGPT, LDH, and uric acid)
6. Pregnancy test (with sensitivity of at least 50 mIU/mL) for women of childbearing potential on Day 7
7. ECG

In addition to the weekly evaluations during the induction cycle, the following evaluations will be conducted at the end of the 3-week treatment cycle:

1. MUGA or ECHO scan or ECHO strain evaluation between Days 18 and 28. Cardiology consultation should be requested if any question arises about cardiac function. The MUGA scan should also be conducted at the Early Termination visit for subjects who are withdrawn prematurely.
2. Bone marrow aspirate and peripheral blood specimens (complete blood count, differential, and platelet count; flow cytometry is optional) between Days 15 and 35 to document response
3. Pregnancy test (with sensitivity of at least 50 mIU/mL) for women of childbearing potential on Day 21
4. Blood sample for cardiac biomarkers on Day 21

6.4 End of Study Evaluations

The subject will return to the clinic for an EOS evaluation within 1 week of their treatment cycle or last study drug administration if the treatment period was prematurely terminated or subject was withdrawn. In addition, any subject with a treatment-related medical event that requires additional follow-up must continue to be monitored as medically appropriate until resolution or stabilization (in the event that resolution is not possible). The procedures listed below are to be undertaken at the EOS visit:

1. ECOG performance status ([Appendix B](#))
2. Blood chemistry (sodium, potassium, chloride, bicarbonate, calcium, magnesium, phosphorus, BUN, creatinine, glucose, albumin, total protein, alkaline phosphatase, total bilirubin, SGOT, SGPT, LDH, and uric acid)
3. CBC with differential and platelet count
4. Monitoring of adverse events and review of concurrent illnesses (treatment-emergent or worsening illness must be recorded as an adverse event)
5. Concomitant medications

6.5 Follow-up Evaluations

Follow-up evaluations will occur 2 weeks after the EOS visit. The procedures listed below are to be undertaken at the Follow-up visit:

1. Physical examination including weight, vital signs, and oral examination
2. Monitoring of adverse events and review of concurrent illnesses (treatment-emergent or worsening illnesses must be recorded as an adverse event). Any subject with a treatment related medical event must continue to be monitored as medically appropriate until resolution or stabilization (in the event that resolution is not possible).
3. Concomitant medications

